## **4.2 Withdrawal of Subjects from the Study**

The duration of the study is defined for each subject as the date a signed written informed consent is provided through the last follow-up visit, up to 42 days following the last IMP infusion.

### **4.2.1 Reasons for Withdrawal/Discontinuation**

Subjects may withdraw from the study at any time and for any reason without prejudice to their future medical care by the investigator or at the study center. Every effort should be made to keep subjects in the study. The reasons for subjects not completing the study will be recorded. A subject may be withdrawn from the study for any of the following reasons:

1. Significant noncompliance with the protocol
2. A serious or intolerable AE(s) that, in the investigator's opinion, requires withdrawal from the study
3. Laboratory safety assessments that reveal clinically significant hematological or biochemical changes from the baseline values
4. Symptoms or an intercurrent illness not consistent with the protocol requirements for study participation or that justifies withdrawal
5. Lost to follow-up
6. Pregnancy
7. The subject withdraws consent or the investigator or sponsor decides to discontinue the subject's participation in the study.

The investigator will also withdraw subjects if Galectin Therapeutics Inc terminates the study. Upon occurrence of a serious or intolerable AE, the investigator will confer with the sponsor. If a subject is discontinued because of an AE, the event will be followed until it is resolved. Any subject may withdraw his or her consent at any time.

## **4.2.2 Handling of Withdrawals**

Subjects are free to withdraw from the study or study treatment at any time upon request. Subject participation in the study may be stopped at any time at the discretion of the investigator or at the request of the sponsor.

Subjects who discontinue study treatment or active participation in the study will no longer receive IMP. When a subject withdraws from the study, the reason(s) for withdrawal shall be recorded by the investigator on the relevant page of the electronic case report form (eCRF). Whenever possible, all subjects who discontinue study treatment or withdraw from the study prematurely will undergo all end-of-study assessments. Subjects who fail to return for final assessments will be contacted by the study center (2 documented telephone calls followed by 1 registered letter) in an attempt to have them comply with the protocol.

It is vital to obtain follow-up data on any subject withdrawn because of an AE or serious AE (SAE). In every case, efforts must be made to undertake protocol-specified, safety, follow-up procedures.

## **4.2.3 Replacements**

Subjects who are randomly assigned to IMP and prematurely discontinued from the study will not be replaced.

## 5 Study Treatments

### 5.1 Method of Assigning Subjects to Treatment Groups

Subjects will be randomly assigned to receive 2 mg/kg lean body weight of GR-MD-02, 8 mg/kg lean body weight of GR-MD-02, or placebo using a 1:1:1 allocation ratio. An interactive web response system (IWRS) will be used to administer the randomization schedule. Unblinded biostatistics personnel not participating in the conduct of the study will generate the randomization schedule using SAS software Version 9.2 or later (SAS Institute Inc, Cary, North Carolina) for IWRS, which will link sequential subject randomization numbers to treatment codes.

The IWRS will send visit notifications to the study center personnel confirming the subject data that were entered. All study visits will have a visit window of  $\pm 3$  days. The IWRS notifications should be filed in source.

### 5.2 Treatments Administered

The GR-MD-02 for injection is supplied in a sterile aqueous solution of phosphate-buffered saline at a concentration of 30 mg/mL GR-MD-02 and should be diluted to the target dose in normal saline and administered intravenously over a period of approximately 60 minutes. The product is expected to be stable at pH 4.0 to 7.5.

GR-MD-02 solution will be supplied in 10-mL vials with the following composition to the study center ([Table 5-1](#)).

**Table 5-1**                      **Composition of GR-MD-02 Concentrate**

Ingredient	Concentration
GR-MD-02	300 mg
USP sodium chloride	82 mg
USP disodium phosphate heptahydrate	14.4 mg
USP monosodium phosphate monohydrate	2.4 mg
USP sterile water for injection	to 10 mL

Instructions on dosing preparation are provided in the Pharmacy Manual.

Once the infusion solutions are prepared, they may be stored at a room temperature (20°C-25°C [68°F-77°F]) and should be administered within 24 hours of preparation. Infusions should be administered intravenously over a period of approximately 60 minutes. Frequency of administration should be once every 2 weeks ([Table 12-2](#)).

### 5.3 Identity of Investigational Medicinal Product

GR-MD-02 (galactoarabino-rhamnogalacturnate) is a soluble polysaccharide composed of an alternating  $\alpha$ -(1,2)-L-rhamnosyl- $\alpha$ -(1,4)-D-galacturonosyl backbone with side branches composed of mainly galactose and arabinose oligosaccharides.

GR-MD-02 for injection is a clear, light yellow-tan solution and is supplied in 10-mL sterile vials at a concentration of 30 mg/mL of GR-MD-02 in phosphate-buffered saline.

Detailed instructions for the preparation and administration of the GR-MD-02 by slow intravenous (IV) drip over a period of approximately 60 minutes will be provided in the Pharmacy Manual.

Lean body mass (LBM) will be used for dosing because it is anticipated that many subjects will be obese and GR-MD-02 is distributed primarily in the blood compartment. Lean body mass will be estimated from height and weight measurements using formulas that have been well-validated in obese individuals ([Janmahasatian 2005](#)):

- Males:  $LBM = 9270 \times TBW / (6680 + 216 \times BMI)$
- Females:  $LBM = 9270 \times TBW / (8780 + 244 \times BMI)$

Total body weight is in kilograms and BMI is in mass (weight in kilograms)/(height in meters). Tables of LBM values for a range of heights and weights will be provided to the pharmacies participating in the study as a check for the calculations.

The study pharmacist at each study center will be unblinded in the preparation of IMP for infusion. Infusion solutions will be prepared as specified in the Pharmacy Manual in IV bags and placed in amber-colored IV bag covers with amber-colored tubing and infusion sets. The amber-colored bags will be sealed with tamper-evident tapes. Once prepared by the unblinded pharmacist, the placebo and drug solutions in the IV infusion set-up will be indistinguishable. Thus, the study subjects, primary investigators, and medical personnel will

be blinded throughout the study as to whether the subject is receiving active drug or placebo. Upon completion of IMP infusion, documentation of the discarded infusion set must be recorded to indicate no unblinding occurred.

## **5.4 Management of Clinical Supplies**

### **5.4.1 Investigational Medicinal Product Packaging and Storage**

Galectin Therapeutics Inc will provide IMP to the study centers. The following drug supplies will be used in the study:

- GR-MD-02, supplied as 10-mL sterile vials
- Placebo (phosphate-buffered saline solution), supplied as 10-mL sterile vials

GR-MD-02 for injection (30 mg/mL) and placebo to be used for the study (phosphate-buffered saline) in 10-mL vials are manufactured by Catalent Pharma Solutions, Woodstock, Illinois, and packaged and labeled for the study center by Catalent Pharma Solutions, Philadelphia, Pennsylvania.

The GR-MD-02 for injection (30 mg/mL) vials and placebo vials are to be stored under refrigerated conditions at 2°C to 8°C (36°F-46°F) until preparation of the drug infusion solution. To prepare the final infusion solution for administration, the GR-MD-02 will be diluted in sterile normal saline as required to achieve the target dose. Instructions on dosing preparation are provided in the Pharmacy Manual.

### **5.4.2 Test Article Accountability**

The investigator will maintain accurate records of receipt of all test articles, including dates of receipt. In addition, accurate records will be kept regarding when and how much test article is dispensed and used by each subject in the study. Reasons for departure from the expected dispensing regimen must also be recorded. Upon completion of IMP infusion, documentation of the discarded infusion set must be recorded to indicate no unblinding occurred. At the completion of the study, to satisfy regulatory requirements regarding drug accountability, IMP will be reconciled and retained or destroyed according to applicable regulations.

### 5.4.3 Other Supplies

In addition to drug and placebo for the study, each study center will also be provided sterile syringe filters, amber-colored bag covers (with tamper-evident tape) and amber-colored infusion tubing sets. See the Pharmacy Manual for the specifications and details regarding these ancillary supplies.

## 5.5 Overdose Management

An overdose is any dose of study treatment given to a subject or taken by a subject that exceeds the dose described in the protocol. Any overdose, with or without associated AEs, must be promptly reported to PPD Pharmacovigilance:

- **SAE [contact]**
- **SAE Fax line: [name]**

Overdoses without signs or symptoms do not need to be recorded as AEs; in case of any AEs associated with the overdose, these should be reported in relevant AE/SAE sections in the eCRF.

### 5.5.1 Treatment of Overdose

There are no known or anticipated adverse effects of GR-MD-02 overdose. The subject should be observed, but there are no specific therapies to be instituted.

### 5.5.2 Medication Errors

A medication error is any unintentional error in prescribing, dispensing, or administration of the IMP. The IMP will be prepared and administered at the study center by trained personnel, thereby reducing the risk of medication errors.

Acceptable treatment windows for infusions will be  $\pm 3$  days. Infusions given outside of accepted windows will be considered “out-of-window” doses. If a dose is out of window, the subject should be brought back into compliance with his or her visit dosing schedule. The subject should not dose within 7 days of the previous or next dose unless the medical monitor is consulted and agrees.

Any AEs resulting from medication errors will be recorded as AEs in the eCRF.

### **5.5.3 Treatment of Medication Errors**

Should a medication error occur, the subject should be observed; however, there are no specific therapies to be instituted.

### **5.6 Misuse for Illegal Purposes**

GR-MD-02 does not have known effects that may be addictive and there are no other known reasons for misuse.

### **5.7 Blinding**

The aqueous solution of GR-MD-02 is light yellow-tan. It has not been possible to match the color with a placebo formulation. Therefore, the study pharmacist at each study center will be unblinded in the preparation of IMP for infusion. The formulated 10-mL solutions will be prepared for infusion as specified in the Pharmacy Manual in IV bags and placed in amber-colored IV bag covers with amber-colored tubing and infusion sets. The amber-colored bags will be sealed with tamper-evident tape. Placebo and drug solutions to be administered in the IV infusion set up are indistinguishable. Thus, the study subjects, primary investigators, and medical personnel will be blinded to the identity of the administration. Infusion of the IMP causes no local reaction in animal studies or in humans participating in the Phase 1 clinical study and, therefore, should not affect blinding.

#### **5.7.1 Breaking the Blind**

A subject's treatment assignment will not be broken until the end of the study unless medical treatment of the subject depends on knowing the study treatment the subject received. In the event that the blind needs to be broken because of a medical emergency, the investigator may unblind an individual subject's treatment allocation. As soon as possible, the investigator should first contact the medical monitor to discuss the medical emergency and the reason for revealing the actual treatment received by that subject. The treatment assignment will be unblinded by the investigator through IWRS. Reasons for treatment unblinding must be clearly explained and justified in the eCRF. The date on which the code was broken together with the identity of the person responsible must also be documented.

## 5.8 Treatment Compliance

Subject compliance will be determined by infusion records.

Acceptable windows for IMP dosing are  $\pm 3$  days. Infusions given outside of accepted windows will be considered “out-of-window” doses. If a dose is out of window, the subject should be brought back into compliance with his or her visit dosing schedule. The subject should not dose within 7 days of the previous or next dose unless the medical monitor is consulted and agrees.

## 5.9 Prior and Concomitant Therapy

Use of all concomitant medications will be recorded in the subject’s eCRF. The minimum requirement is that drug name, reason for use, dose, and the dates of administration will be recorded. This will include all prescription drugs, herbal products, vitamins, minerals, and over-the-counter medications. Any changes in concomitant medications will also be recorded in the subject’s eCRF.

All prior treatments for liver cirrhosis and NASH will be recorded in the eCRF. All other concomitant medications taken from 30 days prior to screening and throughout the entire duration of the subject’s participation in the study will be documented in the eCRF.

Concomitant medications are defined as medications taken any time after the start of exposure to IMP. Prior medications are defined as nonstudy medications discontinued prior to the start of exposure to IMP.

Any concomitant medication deemed necessary for the welfare of the subject during the study may be given at the discretion of the investigator. If prohibited medications are needed for the welfare of the subject, the subject should be discontinued from the study. It is the responsibility of the investigator to ensure that details regarding the medication are recorded in full in the eCRF.

## 5.10 Prohibited Medications or Therapies

Excluded from use are drugs with a narrow therapeutic window metabolized by CYP3A4, including specifically the fast-acting opioids alfentanil and fentanyl; the immunosuppressive drugs cyclosporine, sirolimus, and tacrolimus; the cardiovascular agents ergotamine, quinidine, and dihydroergotamine; and the psychotropic agent pimozide. In vitro experiments

have shown some inhibition of CYP3A4 enzyme expression and activity at levels of drug exposure much higher than obtained in this study. A human drug-drug interaction study is being conducted to evaluate whether there are any changes in in the pharmacokinetics of a model CYP3A4-metabolized drug. Once the results of this study are available, this exclusion criterion may be modified.

Nonselective  $\beta$ -adrenergic inhibitors for the purpose of treatment of portal hypertension are prohibited during the study as well as any off-label drugs.

## 6 Study Assessments and Procedures

Supplementary study conduct information not mandated to be present in this protocol is provided in the accompanying Study Manual/Investigator Site File Notebook which will provide the study center personnel with administrative and detailed technical information that does not impact subject safety.

Before any study procedures are performed, all potential subjects will sign an ICF. Subjects will have the opportunity to have any questions answered before signing the ICF. The investigator must address all questions raised by the subject. The investigator will also sign the ICF.

The schedule of events for prescreening and screening is provided in [Table 12-1](#), for randomization, treatment phase, and follow-up in [Table 12-2](#), and for the end-of-study telephone contact in [Table 12-3](#).

### 6.1 Study Visits

#### 6.1.1 Prescreening Visit (Week -9)

After the subject has provided informed consent, the following information will be collected ([Table 12-1](#)):

- Enter the IWRS and register subject visit data.
- NASH diagnosis: Subjects who have had a previous liver biopsy with a diagnosis of NASH with either advanced bridging fibrosis (Ishak stage 4) or cirrhosis (Ishak stage 5 or 6) are eligible to move forward to screening.
- Conduct a FibroScan: Subjects with a presumptive clinical diagnosis of NASH (based on the assessment of the principal investigator) will have a FibroScan to assess the potential of fibrosis. Subjects who have a FibroScan score of  $\geq 12.0$  kPa will be considered to have advanced fibrosis and will proceed to screening. Likewise, subjects with a documented qualifying FibroScan score within the previous 12 months of screening may proceed to screening.

### **6.1.2 Screening Visit (Week -8 to Day 0)**

The screening visit window is up to 8 weeks after the prescreening visit. Subjects who fail to meet eligibility criteria within this 8-week period due to an abnormal laboratory result may undergo retesting of the abnormal laboratory parameter during the screening window and at the discretion of the investigator and with prior approval of the medical monitor. During the screening visit, the following information will be collected ([Figure 3-2](#) and [Table 12-1](#)):

- Enter the IWRS and register subject visit data.
- Inclusion/exclusion criteria include AUDIT alcohol consumption questionnaire. The AUDIT is a screening tool to identify the early signs of hazardous and harmful drinking and identify mild dependence. This questionnaire (10 questions total) will be given to the subject at the beginning of the screening visit and will be considered source documentation. The subject will sign and date the questionnaire upon completion.
- Collect demographic information.
- Collect medical, surgical, and medication history (concomitant medications taken from 30 days prior to screening).
- Perform a 12-lead ECG assessment.
- Perform hematology testing.
- Perform blood chemistry testing.
- Perform coagulation profile.
- Obtain MELD score.
- Perform viral hepatitis B and C serology.
- Perform HIV serology.

- Perform urine drug screen for amphetamines, cocaine, and nonprescription opiates.
- Perform urinalysis testing.
- Perform serum pregnancy test (females of childbearing potential only).
- Perform chest radiograph (posterior-anterior and lateral views).
- Obtain Child-Turcotte-Pugh score and class (A, B, or C).
- Perform a complete physical examination (including height [in centimeters] and weight [in kilograms]) with particular attention to examination for stigmata of liver disease/cirrhosis.
- Collect vital sign measurements (including heart and respiratory rate, blood pressure, and body temperature).
- Perform MBT (if available) prior to EGD, HVPG, or liver biopsy (at the discretion of the investigator).
- EGD  
Subjects will have had an EGD within 2 months prior to randomization. Subjects with medium or large varices or varices with red signs (red wale marks or red spots), regardless of size, will be excluded from study participation. Subjects without varices or with small varices will continue to HVPG measurement and liver biopsy.
- Obtain demographic information.
- HVPG  
Subjects must have both an HVPG measurement  $\geq 6$  mm Hg and a liver biopsy with advanced bridging fibrosis (Ishak stage 4) or cirrhosis (Ishak stage 5 or 6), presumably due to NASH. Subjects without varices or with small varices will have hepatic venous catheterization with measurement of both wedged and free hepatic venous pressures and standardized calculation of the HVPG prior to randomization and first IMP infusion.

- Obtain liver biopsy  
Liver biopsy may be obtained via a percutaneous approach or a transjugular approach during the HVPG procedure, at the preference of the investigator.
- AE monitoring.

### **6.1.3 Treatment Phase**

#### **6.1.3.1 Randomization**

Randomization must occur between 3 and 8 weeks after screening has begun. The IWRS will be used to administer the randomization schedule.

Prior to Infusion Visit 1, subjects with portal hypertension and the appropriate biopsy will be randomly assigned (1:1:1) to receive 1 of 3 treatment assignments: placebo, GR-MD-02 in dose of 2 mg/kg lean body mass, or GR-MD-02 in a dose of 8 mg/kg lean body mass. Subjects will be entered into the study and randomly assigned if they have both an HVPG screening measurement greater than or equal to 6 mm Hg and a liver biopsy with advanced bridging fibrosis (Ishak stage 4) or cirrhosis (Ishak stage 5 or 6), presumably due to NASH and meet all inclusion criteria and no exclusion criteria.

#### **6.1.3.2 Two Weeks Prior to Infusion Visit 1**

Within 2 weeks prior to the first infusion, a FibroScan will be conducted.

#### **6.1.3.3 Infusion Visit 1 (Week 1)**

During the Infusion 1 Visit, the following procedures and assessments will be performed after randomization and prior to administration of IMP ([Table 12-2](#)):

- Enter the IWRS and register subject visit data.
- CLDQ (This questionnaire will be given to the subject at the beginning of the visit and will be considered source documentation.)
- Alcohol timeline followback (TLFB) (This will be given to the subject at the beginning of the visit and will be considered source documentation.)

- Perform a limited physical examination (including weight and examination of the heart, lung, and abdomen).
- Collect vital sign measurements (including heart and respiratory rate, blood pressure, and body temperature).
- Perform hematology testing.
- Perform blood chemistry testing.
- Collect biomarkers blood sample (will include the ELF test and FibroTest [FibroSure], and galectin-3).
- Collect plasma and serum sample for storage at  $-20^{\circ}\text{C}$ .

The following information will be collected after IMP administration:

- AE monitoring.
- Record concomitant medications.

The following will be performed 2 hours after the end of the IMP infusion:

- Collect PK sample.

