#### **6.1.3.4 Infusion Visits 2, 3, 4, 5, and 6 (Weeks 3, 5, 7, 9, and 11 $\pm$ 3 Days, respectively)**

The following procedures and assessments will be performed prior to administration of IMP:

- Enter the IWRS and register subject visit data.
- Alcohol TLFB (This will be given to the subject at the beginning of the visit and will be considered source documentation.) (Infusion Visit 5)
- Assessment of cirrhosis complications (Infusion Visits 3 and 5).
- Perform a limited physical examination (including weight and examination of the heart, lung, and abdomen).

- Collect vital sign measurements (including heart and respiratory rate, blood pressure, and body temperature).
- Perform urine pregnancy test (females of childbearing potential only) (Infusion Visits 3 and 5).

The following information will be collected after IMP administration:

- AE monitoring.
- Record concomitant medications.

The following will be performed 2 hours after the end of the IMP infusion

- Collect PK sample (Infusion Visits 2, 3, and 4)

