#### **6.4.5.2 Eliciting and Documenting Adverse Events**

All AEs (serious and nonserious) will be assessed beginning at screening and up to 42 days after the last dose of IMP.

Serious AEs that occur more than 42 days after the last dose of IMP need not be reported unless the investigator considers them related to IMP.

At every study visit, subjects will be asked a standard nonleading question to elicit any medically related changes in their well-being. They will also be asked if they have been hospitalized, had any accidents, used any new medications, or changed concomitant medication regimens (both prescription and over-the-counter medications).

In addition to subject observations, AEs identified from any study data (eg, laboratory values, physical examination findings, ECG changes) or identified from review of other documents that are relevant to subject safety will be documented on the AE page in the eCRF.

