**Table 12-2 Schedule of Events - Randomization, Treatment Phase, and Follow-up/Early Termination, Continued**

Infusion Visit	0	1	2, 3, 4, 5, 6	7	8, 9, 10, 11, 12	13	14, 15, 16, 17, 18, 19	20	21	22, 23, 24, 25	26	14-28 Days After Final Dose	14 Days After Previous Visit/ET
Week ± 3 days		1	3, 5, 7, 9, 11	13	15, 17, 19, 21, 23	25	27, 29, 31, 33, 35, 37	39	41	43, 45, 47, 49	51	53-55	57
Liver biopsy l												X	
Assessment of cirrhosis complications			X - Inf Visits 3, 5	X	X - Inf Visits 9, 11	X	X - Inf Visits 15, 17, 19		X	X - Inf Visits 23, 25	X		
AE monitoring		X	X	X	X	X	X	X	X	X	X	X	X
Concomitant medications		X	X	X	X	X	X	X	X	X	X	X	X
PK sample k		X	X - Inf Visits 2, 3, 4	X	X - Inf Visit 10	X					X		

Abbreviations: AE, adverse event; TLFB, Timeline Followback; EGD, esophagogastroduodenoscopy; CLDQ, chronic liver disease questionnaire; ECG, electrocardiogram; ET, early termination; HVPG, hepatic venous pressure gradient; IMP, investigational medicinal product; Inf, infusion; IWRS, interactive web response system; MBT, C-methacetin breath test; MELD, model for end-stage liver disease; PK, pharmacokinetic.

Note: Subjects will be entered into the study and randomly assigned to IMP if they have both an HVPG screening measurement  $\geq 6$  mm Hg and a liver biopsy with advanced bridging fibrosis (Ishak stage 4) or cirrhosis (Ishak stage 5 or 6) presumably due to NASH.

Note: Acceptable treatment windows for infusions will be  $\pm 3$  days. Infusions given outside of accepted windows will be considered “out-of-window” doses. If a dose is out of window, the subject should be brought back into compliance with their visit dosing schedule. The subject should not dose within 7 days of the previous or next dose unless the medical monitor is consulted.

Note: Randomization must occur prior to Infusion Visit 1.

a Within 2 weeks prior to the first infusion.

b To be administered at the beginning of the visit.

c Limited physical examination includes weight and examination of the heart, lung, and abdomen.

d Urine pregnancy test will be given to females of childbearing potential every 4 weeks during the treatment phase

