e Vital sign measurements include heart and respiratory rate, blood pressure and body temperature prior to IMP administration. Blood pressure will be obtained with the subject in the supine position and measured twice consecutively with a 1-minute interval between measurements. The average of the 2 measurements will be recorded.

- f Hematology will include complete blood cell count with differential (red blood cells, white blood cells, , red cell indices, platelets, hemoglobin, and hematocrit).
- g Blood chemistry will include alanine aminotransferase, aspartate aminotransferase, albumin, alkaline phosphatase, bicarbonate, blood urea nitrogen, calcium, chloride, creatinine, glucose, lactate dehydrogenase, magnesium, phosphorus, potassium, sodium, total and direct bilirubin, total protein, uric acid,  $\gamma$ -glutamyl transferase, and fasting insulin level. Subjects must be in a fasted state prior to blood collection.
- h Biomarker blood tests will include the enhanced liver fibrosis test, FibroTest (FibroSure), and galectin-3 and will occur prior to first infusion and at Infusion Visits 13 and 14 to 28 days following final 26th infusion.
- i IMP administration will occur after the following procedures: limited physical examination, vital sign measurements, hematology, blood chemistry, and biomarker blood samples.
- j Within 14 to 28 days after the final 26th dose of IMP or where feasible following study termination due to the occurrence of a clinical event or withdrawal of consent. EGD must be performed on a different day within the 14- to 28-day follow-up period than when the HVPG assessment is performed.
- k The PK sample will be collected 2 hours after the end of the IMP infusion.

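### At all 26 infusion visits the adverse-event and medication checks are listed after the dose, and nothing in the protocol places them before it

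*Protocol*

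**What the plan says.** Each infusion-visit section of the protocol (6.1.3.3 to 6.1.3.12) has a list of procedures to be done before the investigational product is given, then a second list headed "The following information will be collected after IMP administration". AE monitoring and the recording of concomitant medications stand in the second list every time.

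The duty to question subjects is set in section 6.4.5.2: "At every study visit, subjects will be asked a standard nonleading question to elicit any medically related changes in their well-being". The same paragraph requires asking whether subjects have "used any new medications, or changed concomitant medication regimens". It does not say whether this comes before or after the infusion.

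Table 12-2 marks both items at every infusion visit without timing. Its footnote i is the one place in the schedule that fixes an order relative to the dose: "IMP administration will occur after the following procedures: limited physical examination, vital sign measurements, hematology, blood chemistry, and biomarker blood samples". Neither the AE question nor the medication question is among the procedures named.

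Section 6 describes the Study Manual as giving "administrative and detailed technical information that does not impact subject safety".

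**The concern.** The answers to these questions bear on whether that day's infusion should go ahead. Section 4.2.1 lists a serious or intolerable AE, and separately an intercurrent illness or symptoms incompatible with participation, as grounds for withdrawal. Section 5.9 says a subject who needs a prohibited medication should be discontinued. Section 5.10 prohibits named narrow-window drugs metabolized by CYP3A4, and nonselective beta-blockers used for portal hypertension. A subject may have developed such an event, or started such a drug, in the two weeks since the previous dose. The questions that would reveal it are listed after the new dose has been given.

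A before-and-after order is written into every visit, so this is more than missing detail: a site working down the list would dose first. The order is relevant to safety, and the protocol reserves the Study Manual for matters that do not affect safety, so it belongs in the protocol.

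A smaller point concerns Visit 1. Asking before the first dose would also help separate events already present from treatment-emergent ones, a distinction the AE analysis depends on.

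**Working it through.** No error-rate or power formula applies. The check is a reading of each visit list, with counts.

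**Number of visits.** Section 3.1 plans 26 infusions. The ten visit sections cover 1 + 5 + 1 + 5 + 1 + 6 + 1 + 1 + 4 + 1 = 26, which agrees.

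**Position of the items.** The cirrhosis-complication assessment is the main pre-dose item that touches on interval symptoms, so its visits are shown alongside.

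| Protocol section | Visits | AE monitoring and concomitant medications | Pre-dose cirrhosis-complication assessment |
|---|---|---|---|
| 6.1.3.3 | 1 | after dose only | none |
| 6.1.3.4 | 2–6 | after dose only | 3, 5 |
| 6.1.3.5 | 7 | after dose only | 7 |
| 6.1.3.6 | 8–12 | after dose only | 9, 11 |
| 6.1.3.7 | 13 | after dose only | 13 |
| 6.1.3.8 | 14–19 | after dose only | 15, 17, 19 |
| 6.1.3.9 | 20 | after dose only | none |
| 6.1.3.10 | 21 | after dose only | 21 |
| 6.1.3.11 | 22–25 | after dose only | 23, 25 |
| 6.1.3.12 | 26 | after dose only | 26 |

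- AE and medication items after the dose only: 26 of 26. Either item before the dose: 0 of 26.
- Pre-dose cirrhosis-complication assessment: 2 + 1 + 2 + 1 + 3 + 1 + 2 + 1 = 13 visits. The first group, for example, reads "Assessment of cirrhosis complications (Infusion Visits 3 and 5").
- Visits without it: 26 − 13 = 13, namely Visit 1 and the even-numbered Visits 2 to 24.
- The chronic liver disease questionnaire (CLDQ) is given before the dose at Visits 1 and 26. If it counts as a symptom item at Visit 1, 13 − 1 = 12 visits have none: 12/26 = 46%. If it does not, the figure is 13/26 = 50%.

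At those 12 even-numbered visits the pre-dose list holds only the web-response entry, the limited examination and vital signs, with blood tests added at Visit 20. The urine pregnancy test does not fall there either; it is scheduled at odd-numbered Visits 3 to 25.

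**Search for a pre-dose placement elsewhere.** Section 6.4.5.2 gives the questions but no timing. Table 12-2 gives the visits but no timing, and footnote i omits both items. The dosing-window text (5.5.2, 5.8), the concomitant and prohibited therapy sections (5.9, 5.10) and the SAP contain no pre-dose AE or medication check.

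**Exposure, for context only.** With no dropout, planned infusions number 156 × 26 = 4,056, of which 156 × 12 = 1,872 fall at the 12 visits. If all of the 25% dropout in section 7.6 occurred before the first dose, 156 × 0.75 = 117 subjects remain, giving 117 × 26 = 3,042 and 117 × 12 = 1,404. These count planned infusions under the listed order. They do not estimate delayed questions or doses wrongly given.

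**The case against.** **The list may govern recording only.** The heading speaks of collecting information, the duty to ask is set separately for every visit, and nothing forbids asking first. That is right as far as it goes. At best, though, it leaves the text ambiguous: two parallel before-and-after lists read naturally as a sequence, and footnote i shows the sponsor fixing pre-dose order for other procedures.

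**Little turns on the answer that day.** Dose modification is not allowed, there is no AE-based rule for holding a dose, and withdrawal for an AE is at the investigator's judgment. The stake is roughly one infusion given before a decision to stop. The documents make that look low risk: no overdose effects known or anticipated (5.5.1), drug measurable only through 72 hours (2.5), and CYP3A4 inhibition seen in vitro at exposure well above that in the study (5.10). All of this stands, and it keeps the point small.

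**Other safeguards exist.** An examination and vital signs, including temperature, precede every dose, cirrhosis complications are assessed before 13 doses, and subjects are told to report symptoms (6.4.5.1). These lower the risk, but none asks about new medications.

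**Visit 1 is a weaker case.** Screening includes AE monitoring and medication history, and eligibility is confirmed before randomization. This is fair. The other 25 visits are unaffected.

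**Unseen or later documents may settle it.** Site manuals were not available. The protocol supplied is the original of 20 February 2015, while the SAP describes a revised design. The count therefore applies to the protocol text supplied. The possibility of a later correction does not change what that text says.

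**Conclusion.** The point holds as a minor safety improvement. At 26 of 26 infusion visits the protocol lists AE monitoring and medication recording only after the dose, and no other section or schedule entry puts the required questions before it. No visit has a pre-dose medication item. Twelve visits (46%) have no pre-dose symptom item, or 13 (50%) if the Visit 1 CLDQ is not counted; these two figures treat the physical examination as something other than a symptom question.

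Confidence is high in the listed order and lower in its practical effect. The documents give no rate of missed or late-discovered events, sites may already ask first, and no harm is shown. The trial's efficacy inference is not affected.

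**What to change.** In sections 6.1.3.3 to 6.1.3.12, add one item to each pre-dose list: ask the section 6.4.5.2 AE and medication questions for the interval since the last visit. Add the same item to footnote i of Table 12-2. Keep a brief AE check after the infusion to pick up infusion reactions.

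This fixes the order of questions already required and creates no stopping rule. The cost is protocol wording, a change to the visit worksheet and a slightly longer visit, because a short check remains after the infusion. No extra visit, sample or staff is needed.
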